9.3. Analysis Sets

Participant Analysis Set	Description
Enrolled	All participants who sign the informed consent form
Safety	All participants who take at least 1 dose of study treatment. This is the primary set for safety analyses
Efficacy-evaluable	Participants in the Safety analysis set with measurable disease at baseline and one of the following: (a) at least 1 post-baseline evaluable tumor assessment, (b) clinical progression, or (c) death
[REDACTED]	[REDACTED]
[REDACTED]	[REDACTED]

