9.5. Interim Analysis

Review of the safety and efficacy data will be performed by the sponsor on an ongoing basis in this study. Assessment of the observed responses will be performed after enrollment of approximately 12 and 20 efficacy-evaluable participants for treatment benefit. If no confirmed response per RECIST v1.1 is observed in approximately the first 12 evaluable participants of a cohort, the recruitment of participants in that cohort will be stopped. If there are ≤ 3 confirmed responses in the first 20 evaluable participants of a cohort, the recruitment of participants in the cohort will be stopped. There will be no pause in enrollment during the interim analysis of the first 12 evaluable participants of a cohort, and the futility boundary will be adjusted based on the actual number of participants at each stage.

Interim futility monitoring will be implemented through the BPP approach with the prior distribution for ORR assumed to be Beta (0.5, 0.5). Table 10 has the operating characteristics for futility of stopping at 12 and 20 participants. If no response is observed in the first 12 participants of a cohort, there is an 89% posterior probability that the actual response rate is

no more than 10%. If there are ≤ 3 responses in the first 20 participants of a cohort, there is a 70% posterior probability that the actual response rate is no more than 20%.

Table 10: Posterior Probability for Interim Futility Monitoring

No Participants	Futility Stopping	Prob ($\theta \leq 10\% r, n$)	Prob ($\theta \leq 15\% r, n$)	Prob ($\theta \leq 20\% r, n$)
12	0	89%	95%	98%
20	1	76%	91%	97%
20	2	46%	72%	87%
20	3	21%	47%	70%

θ = True response rate; r = the observed responses; n = the number of participants

The SAP will describe the planned interim analyses in greater detail.

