10.1.5. Safety Monitoring

Throughout the study, the sponsor will perform safety assessments of all enrolled participants on an ongoing basis. A thorough evaluation of the safety and efficacy will be performed after enrollment of the first 12 participants to determine whether to continue or stop a cohort.

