#### 5.5. Interim Analysis

Review of the safety and efficacy data will be performed by the sponsor on an ongoing basis in this study.

Assessment of the observed responses will be performed after enrollment of approximately 12 and 20 efficacy-evaluable participants for treatment benefit. If no confirmed response per RECIST v1.1 is observed in approximately the first 12 evaluable participants of a cohort with at least two post-baseline evaluable tumor assessments, the recruitment of participants in that cohort will be stopped. If there are  $\leq 3$  confirmed responses in the first 20 evaluable participants of a cohort, the recruitment of participants in the cohort will be stopped. There will be no pause in enrollment during the interim analysis of the first 12 evaluable participants of a cohort, and the futility boundary will be adjusted based on the actual number of participants at each stage.

Interim futility monitoring will be implemented through the Bayesian Posterior Probability (BPP) approach with the prior distribution for ORR assumed to be Beta (0.5, 0.5). [Table 5](#) has the operating characteristics for futility of stopping at 12 and 20 participants.

If no response is observed in the first 12 participants of a cohort, there is an 89% posterior probability that the actual response rate is no more than 10%. If there are  $\leq 3$  responses in the first 20 participants of a cohort, there is a 70% posterior probability that the actual response rate is no more than 20%.

Jazz Pharmaceuticals, Inc.

JZP712-201 Statistical Analysis Plan - Protocol Amendment

2

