## 6. ANALYSIS SETS

For purposes of analysis, the following populations are defined:

Analysis Set	Description
Enrolled	All participants who sign the informed consent form (ICF).
Safety	All participants who took at least one dose of study treatment. This is the primary set for safety analyses.
Efficacy evaluable	Participants in Safety analysis set with measurable disease at baseline and one of the following: (a) at least one post-baseline evaluable tumor assessment, (b) clinical progressions, or (c) death.
[REDACTED]	[REDACTED]
[REDACTED]	[REDACTED]

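### The n = 20 futility rule lets recruitment be stopped on a count of confirmed responses while some of the 20 have had only one scan and cannot yet have one

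*SAP*

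**What the plan says.** Protocol 9.5 and SAP 5.5 set the timing of the looks by a number of participants: "Assessment of the observed responses will be performed after enrollment of approximately 12 and 20 efficacy-evaluable participants for treatment benefit". Neither gives a minimum follow-up time for the looks.

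Evaluability is defined in Protocol 9.3 and SAP 6. Beyond a dose of study drug and measurable disease at baseline, a participant needs one of: "a) at least one post-baseline evaluable tumor assessment, (b) clinical progressions, or (c) death".

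At the second look the action is fixed. With three or fewer "confirmed responses in the first 20 evaluable participants of a cohort, the recruitment of participants in the cohort will be stopped". At the first look, recruitment stops if there is no confirmed response, and the SAP bases that count on "the first 12 evaluable participants of a cohort with at least two post-baseline evaluable tumor assessments". The two-assessment condition is absent from the SAP's n = 20 sentence and from both sentences in Protocol 9.5.

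Confirmation means repeat imaging at least 4 weeks after the response is first seen (Protocol Appendix 8). Scans are every 6 weeks through Week 36, with the first due at Week 6 ± 7 days (Protocol 4.1, SAP 9.1.1).

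**The concern.** A participant can enter the denominator about 6 weeks before being able to enter the numerator. A response seen at the first scan (Week 5 to 7) can be confirmed at Week 9 to 11 at the earliest, and at about Week 12 on the scheduled scans. If the look is taken when the 20th participant becomes evaluable, everyone enrolled shortly before counts as a non-responder, including anyone with an unconfirmed response on the first scan.

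The n = 20 look is the more exposed of the two, since continuing takes 4 confirmed responses rather than 1, yet it is the look without the SAP's safeguard. Nothing else fills the gap. The 6-month follow-up rule (Protocol 9.4, SAP 7) governs the primary analysis, and the boundary adjustment in Protocol 9.5 and SAP 5.5 is for the number of participants, not for follow-up. Neither document says how to treat a response awaiting its confirmatory scan at this look.

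At stake is the expansion of a cohort whose response rate is at or above the 20% that Protocol 4.2 calls desirable. OS follow-up also ends for a cohort closed for futility (Protocol 4.1, SAP 5.1).

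**Working it through.** **1. The plan's own figures.** With a Beta(0.5, 0.5) prior and r responses in n, the posterior is Beta(0.5 + r, 0.5 + n − r).

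- n = 20, r = 3: P(θ ≤ 20%) from Beta(3.5, 17.5) = 0.697. The plan states 70%.
- n = 12, r = 0: P(θ ≤ 10%) from Beta(0.5, 12.5) = 0.892. The plan states 89%.

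Both reproduce, and both treat every outcome as final.

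**2. Some outcomes not yet final.** Let k be the number of the first 20 enrolled too recently to have a confirmed response. The documents do not give k, so a range is shown. These k participants are taken to add no information to the count.

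- P(stop) = P(Binomial(20 − k, p) ≤ 3), where p is the true ORR.
- Posterior at 3 responses: P(θ ≤ 20%) from Beta(3.5, 17.5 − k).

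Examples at p = 20%:

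- k = 0: 0.0115 + 0.0576 + 0.1369 + 0.2054 = 0.411
- k = 4: 0.0281 + 0.1126 + 0.2111 + 0.2463 = 0.598

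| k | P(stop), ORR 20% | P(stop), ORR 30% | P(stop), ORR 40% | P(θ ≤ 20%), 3 responses |
|---|---|---|---|---|
| 0 | 41.1% | 10.7% | 1.6% | 70% |
| 2 | 50.1% | 16.5% | 3.3% | 62% |
| 4 | 59.8% | 24.6% | 6.5% | 52% |
| 6 | 69.8% | 35.5% | 12.4% | 42% |
| 8 | 79.5% | 49.2% | 22.5% | 31% |

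A cohort that stops with mature data also stops with immature data. The difference from the k = 0 row is therefore the chance of a stop that full follow-up of the same 20 would have reversed. At ORR 30% and k = 4 it is 24.6% − 10.7% = 13.9%.

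**3. From accrual to P(stop).** Assumptions, none of them in the documents: random (Poisson) accrual; responders first respond at Week 6, 12 or 18 in 60%, 30% and 10%; confirmation 4 or 6 weeks later; look taken at the 20th participant's Week 6 scan. Simulated P(3 or fewer confirmed), with 4-week then 6-week confirmation (repeat runs differ by up to about a point):

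| Accrual per month per cohort | ORR 20% | ORR 30% |
|---|---|---|
| 0.5 | 49%, 50–51% | 16%, 17% |
| 1 | 53%, 55% | 19%, 21% |
| 2 | 61%, 65% | 27%, 32% |
| 4 | 76%, 83% | 47%, 59% |
| Full follow-up (exact) | 41% | 11% |

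**The case against.** The strongest reply is that the text permits an early count but does not require one. No look date is fixed, the rule counts confirmed responses, and its rationale presumes known outcomes, so a careful sponsor would wait. The SAP's two-assessment phrase might even be read as carrying over to the next sentence. There is also little pressure to hurry: 20 is the planned end of the initial stage, and the no-pause sentence concerns only the first 12. This stands against a reading that a reader might infer, namely that the rule as written closes cohorts because follow-up is short. The documents show only that nothing prevents it. The carry-over reading is arguable at best for the SAP, and is not available in Protocol 9.5, which has no such phrase.

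A reader might also infer that the reported ORR is biased. The documents do not support that. The rule ends recruitment; it does not itself end treatment or scanning. The primary analysis waits for 6 months of treatment and follow-up in the last enrolled participant, so late confirmations can still count.

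The size is also open to challenge. Accrual and response timing are assumed, and the figures of 83% and 59% are upper-end cases. The 41% is the design's own stop rate at a true ORR of 20% and has nothing to do with immaturity. Participants who are evaluable through progression or death are true non-responders and are unaffected.

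Protocol 10.1.5 might seem to add support, but it concerns only the first 12 participants and says nothing about n = 20.

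**Conclusion.** The gap is real. As written, the n = 20 rule allows a mandatory recruitment stop while some of the 20 have had one scan and cannot yet have a confirmed response. The SAP guards against this at n = 12 only, and the protocol at neither look. The quoted 70% posterior does not describe such a count.

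The direction needs no timing assumption; the size does. Under the assumptions in step 3, the probability of stopping rises from 41% to somewhere between about 49–51% and 76–83% at a true ORR of 20%, and from 11% to between about 16–17% and 47–59% at 30%, as accrual goes from 0.5 to 4 per month. A look taken later than the 20th participant's first scan would reduce these increases. The consequence is a possibly missed expansion and, if the cohort is closed for futility, the end of its OS follow-up. The change is worth making because it is cheap and the stop is mandatory.

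**What to change.** In Protocol 9.5 and SAP 5.5, use the same wording for both looks:

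- Apply the rule to the first 12 or 20 participants of the Efficacy-evaluable set once each has had at least two post-baseline tumor assessments, or has earlier progressed, died, started new anticancer therapy or left the study.
- Keep all of them in the denominator, as non-responders unless a response is already confirmed.
- Declare no stop while unconfirmed responses awaiting their confirmatory scan could still bring the count to the continue threshold (1 at n = 12, 4 at n = 20).

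Copying the SAP's n = 12 phrase to n = 20 would not do. Read literally, "with at least two post-baseline evaluable tumor assessments" drops early progressions and deaths and raises the observed ORR. It also leaves open a response first seen at the second scan. The two-assessment cut-off is deliberate: without one, a participant with stable disease could hold the decision open indefinitely. The price is that a first response at a third or later scan may be missed at the look.

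The cost is one paragraph in each document and a later decision: about one scan interval (6 weeks), or two if a response is first seen at the second scan. If recruitment is not paused, 6 weeks is about 1.4 months, which is 0.7 extra participants at 0.5 per month (1.4 × 0.5) and between 5 and 6 at 4 per month (1.4 × 4 = 5.6).

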**Table 5: Posterior Probability for Interim Futility Monitoring**

No Participants	Futility Stopping	Prob ( $\theta \leq 10\%   r, n$ )	Prob ( $\theta \leq 15\%   r, n$ )	Prob ( $\theta \leq 20\%   r, n$ )
12	0	89%	95%	98%
20	1	76%	91%	97%
20	2	46%	72%	87%
20	3	21%	47%	70%

$\theta$  = True response rate;  $r$  = the observed responses;  $n$  = the number of participants

## 6. ANALYSIS SETS

For purposes of analysis, the following populations are defined:

Analysis Set	Description
Enrolled	All participants who sign the informed consent form (ICF).
Safety	All participants who took at least one dose of study treatment. This is the primary set for safety analyses.
Efficacy evaluable	Participants in Safety analysis set with measurable disease at baseline and one of the following: (a) at least one post-baseline evaluable tumor assessment, (b) clinical progressions, or (c) death.
[REDACTED]	[REDACTED]
[REDACTED]	[REDACTED]

## 7. GENERAL ASPECTS FOR STATISTICAL ANALYSIS

The statistical principles applied in the design and planned analyses of this study are consistent with International Conference on Harmonization (ICH) E9 guidelines ([ICH 1998](#)). [Section 5.5](#) describes the planned interim assessment of the observed response and decision process following the interim assessment. The primary analysis is planned to take place when the last enrolled participant in a cohort has had 6 months of treatment and follow-up. The primary analysis described in this SAP may be performed separately for each cohort based on enrollment.

### 7.1. General Methods

The efficacy analyses will be performed using the Efficacy evaluable analysis set, separately for each cohort. The safety analyses will be performed using the Safety analysis set by cohort and across cohorts. By-participant listings will be generated by cohort and across cohorts.

Jazz Pharmaceuticals, Inc.

JZP712-201 Statistical Analysis Plan - Protocol Amendment

2

Unless otherwise specified, continuous data will be summarized using descriptive statistics comprising of the number of participants with data to be summarized (n), mean, standard deviation (SD), median, minimum (min) and maximum (max). Categorical variables will be tabulated by the frequency and proportion of participants falling into each category.

All summaries, statistical analyses, data listings and figures will be completed using version 9.4 of the Statistical Analysis System (SAS Institute, North Carolina, USA) unless otherwise noted. All figures will be generated with high resolution in black and white. Each summary, figure or data listing will include the data cutoff date in addition to the production date.

## 7.2. Baseline, Post Baseline, and Study Day Definitions

### 7.2.1. Baseline

Baseline evaluations are defined as evaluations with a date on or prior to the date of the first dose of study treatment. If there are multiple valid observations in the Screening Period, then the latest non-missing observation on or before the first dose of study treatment will be used as the baseline for analyses.

### 7.2.2. Post-Baseline

Post baseline evaluations are defined as evaluations taken after the date of the first dose of study treatment.

The post-baseline period is further characterized into:

- A treatment period, which is the time period from the date of the first dose to the date of the last dose of study treatment
- A 30-day safety follow-up period after the last dose of study treatment
- An OS follow-up period, which is the period following the 30-day safety follow-up period after the last dose of study treatment until participants die or withdraw consent or are lost to follow-up or the cohort closes. If a participant is to permanently discontinue study intervention before disease progression, the participant will be followed for survival by telephone visits every 3 months until at least 80% of participants in each cohort have died, withdrawn consent, or are lost to follow-up.

### 7.2.3. Study Day

The day of receiving the first dose of study treatment is defined as Study Day 1 or Day 1. All other study days will be computed relative to Day 1. Day 0 will not be used. The day before receiving the first dose of study treatment is Day -1 and the day after receiving the first dose of study treatment is Day 2. The following computation rules will be used:

- For events on or after Day 1, study day for a particular event or visit will be calculated as:  $\text{Date}_{\text{event}} - \text{Date}_{\text{Day 1}} + 1$ .
- For events before Day 1, study day for a particular event will be calculated as:  $\text{Date}_{\text{event}} - \text{Date}_{\text{Day 1}}$ .

Jazz Pharmaceuticals, Inc.

JZP712-201 Statistical Analysis Plan - Protocol Amendment

2

#### 7.2.4. Visit Windows

Analysis Visit windowing in general will not be applied. In the case of a retest (same visit number assigned), the latest available test results as provided in the data transfer for that visit/time point will be used for by-visit summaries.

A 30-day safety follow-up period after the last dose of study treatment will be considered for assessing treatment-emergent adverse events (TEAEs).

All scheduled and unscheduled visits will be included in by-participant listings.

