5.5. Criteria for Treatment Continuation

Further treatment cycles (ie, Cycle 2 and after) will be administered Q3W if the participant fulfills all the retreatment criteria within 3 days prior to the scheduled lurbinectedin infusion (Table 3) and defined in Table 4.

Table 4: Criteria for Treatment Continuation (Cycle 2 and After)

Variable	Retreatment Criteria (Day 1)
Hemoglobin ^a	≥ 9 g/dL
ANC	≥ 1.5 × 10 ⁹ /L
Platelets	≥ 100 × 10 ⁹ /L
AST/ALT	≤ 3 × ULN; for participants with documented metastatic liver disease, AST and ALT levels ≤ 5 × ULN
Total serum bilirubin	≤ 1.5 × ULN
Serum creatinine	≤ 1.5 × ULN or creatinine clearance ≥ 30 mL/min
Events of rhabdomyolysis	Withhold for Grade 2; resume at same dose if Grade ≤ 1
Other nonhematological treatment-related AEs (except isolated increased GGT and/or AP; Grade 2 asthenia, constipation, alopecia, peripheral neuropathy, or nonoptimally treated nausea and/or vomiting)	Grade ≤ 1
Active infection (including sepsis) and/or bleeding (any grade)	Absence

Abbreviations: AE = adverse event; ALT = alanine aminotransferase; ANC = absolute neutrophil count; AP = alkaline phosphatase; AST = aspartate aminotransferase; GGT = gamma-glutamyltransferase; ULN = upper limit of normal.

^a Participants may receive packed red blood cells transfusion and/or erythropoietin treatment, if clinically indicated, to increase or maintain adequate hemoglobin levels.

If a participant does not meet the requirements for treatment continuation on Cycle 2 Day 1 or subsequent cycles, reassessments will be performed at least every 48 to 72 hours for evaluation of treatment continuation. Treatment can be withheld up to a maximum of 3 weeks. Lurbinectedin dose delay and reduction rules are presented in Section 6.7.

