8.3.4. Clinical Safety Laboratory Assessments

- See Appendix 3 for the list of clinical laboratory tests to be performed and to the SoA (Table 3) for the timing and frequency.
- The investigator must review the laboratory report, document this review, and record any clinically significant changes occurring during the study as an AE. The laboratory reports must be filed with the source documents.
- Abnormal laboratory findings associated with the underlying disease are not considered clinically significant unless judged by the investigator to be more severe than expected for the participant's condition.
- All laboratory tests with abnormal values considered clinically significant during participation in the study and/or considered by the investigator to be related to study drug should be repeated until the values return to normal or baseline or are no longer considered clinically significant by the investigator.
 - If clinically significant values do not return to normal/baseline within a period of time judged reasonable by the investigator, the etiology should be identified, and the sponsor notified.
 - All protocol-required laboratory tests, as defined in Appendix 3, must be conducted in accordance with the SoA (Table 3).

- Any participants with febrile neutropenia of any grade, Grade 4 neutropenia, and/or Grade 4 thrombocytopenia, should have relevant tests repeated daily until recovery to Grade ≤ 3 and through the day after fever resolution, if applicable.
- For Cycle 3 and after, Hematology and Biochemistry “A” tests on Days 8 and 15 are to be performed only in participants with Grade ≥ 3 biochemical or Grade 4 hematological treatment-related toxicities, or who required dose adjustments due to hematological or biochemical abnormalities in the preceding cycle (Table 3).

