Clinical laboratory results will be graded according to CTCAE criteria, CTCAE v5.0 criteria (Appendix 2). The frequency and percentage of participants with each CTCAE grade for each visit during the treatment period will be described by cohort. Both the scheduled and unscheduled assessments will be used to identify the worst post-baseline values.

Listings of all laboratory data with results reported using SI and Conventional units, normal reference ranges, and CTCAE grades (when possible) will be provided using Safety analysis set.

Pregnancy test results and other screening tests will be included in by-participant listings only.

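### The latest-retest rule in SAP 7.2.4 favours the lower grade in the by-visit laboratory grade table, and can drop Grade 4 counts where repeats share the scheduled visit number

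*SAP*

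**What the plan says.** Three sets of rules meet here.

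- **Which result is summarised.** SAP 7.2.4 generally applies no visit windows. Its one selection rule is for repeats that carry the same visit number: "the latest available test results as provided in the data transfer for that visit/time point will be used for by-visit summaries". Scheduled and unscheduled visits are both kept in the listings.
- **When tests are repeated.** Under Protocol 8.3.4, participants with febrile neutropenia, Grade 4 neutropenia or Grade 4 thrombocytopenia "should have relevant tests repeated daily until recovery to Grade ≤ 3 and through the day after fever resolution, if applicable". Other abnormal results judged clinically significant or drug-related "should be repeated until the values return to normal or baseline or are no longer considered clinically significant by the investigator". Under Protocol 5.5, if the Day 1 criteria for the next cycle are not met, "reassessments will be performed at least every 48 to 72 hours for evaluation of treatment continuation", and treatment can be withheld for up to 3 weeks.
- **What is tabulated.** SAP 10.3 plans one laboratory grade table: "The frequency and percentage of participants with each CTCAE grade for each visit during the treatment period will be described by cohort". The next sentence adds: "Both the scheduled and unscheduled assessments will be used to identify the worst post-baseline values". No table is named that would display those worst values.

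**The concern.** The retests are not a random second look. A bad value starts the series, and an acceptable value usually ends it. A rule that keeps the last value of such a series selects on the outcome, and in the favourable direction.

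This matters because Protocol 2.3.1 names reversible myelosuppression as the main risk, safety is a secondary objective, and Protocol 4.1 allows a cohort to expand beyond 20 only if there are no safety concerns. The by-visit table is the only laboratory grade summary that the SAP text describes, and it is by cohort. Its Grade 4 column should not depend on how a site or data manager numbers a repeat sample.

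**Working it through.** The plan states no figure that depends on this rule, so there is none to reproduce. The check traces the rules and then illustrates the scale.

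**Tracing the rules**

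1. *Grade 4 count at a scheduled visit, repeats filed under the same visit number.* Repeats run daily until Grade 3 or lower, so the last value of a completed series is not Grade 4. SAP 7.2.4 selects that value and the Grade 4 result leaves the by-visit table. Loss for that episode: 100%. The value shown may still be Grade 3.
2. *Same count, repeats entered as unscheduled visits.* The condition in SAP 7.2.4 is not met and the scheduled Grade 4 result stays. Loss from the rule: 0%.
3. *Day 1 criteria not met, reassessments filed under the Day 1 number.* Protocol Table 4 requires ANC of at least 1.5 × 10⁹/L and platelets of at least 100 × 10⁹/L. In SAP Appendix 2, Grade 2 starts below 1.5 for neutrophils and below 75 for platelets. A participant who clears the criteria is therefore shown at Grade 1 or better on both, whatever count delayed the dose. One who never clears them is shown with a failing value.
4. The same selection feeds the by-visit means and changes from baseline in SAP 10.3.

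**Scale (illustration only)**

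Inputs:
- p = 0.124, the Grade 4 neutropenia rate that Protocol 2.2.2 quotes from an earlier study with 32 treated patients. The nearest whole count, 4/32 = 12.5%, agrees to 0.1 percentage point.
- n = 20 (one cohort) and n = 60 (three cohorts), from Protocol 9.2.
- f = share of Grade 4 episodes whose repeats carry the scheduled visit number. The documents do not give it, so it is varied from 0 to 1.
- Assumption: each affected participant has one Grade 4 episode, found at a scheduled visit, with a completed repeat series.

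Formulas: expected with Grade 4 = n × p; shown by visit = n × p × (1 − f); lost = n × p × f.

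n × p = 20 × 0.124 = 2.48, and 60 × 0.124 = 7.44.

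| f | Shown, n = 20 | Lost, n = 20 | Shown, n = 60 | Lost, n = 60 |
|---|---|---|---|---|
| 0 | 2.48 | 0 | 7.44 | 0 |
| 0.25 | 1.86 | 0.62 | 5.58 | 1.86 |
| 0.5 | 1.24 | 1.24 | 3.72 | 3.72 |
| 1 | 0 | 2.48 | 0 | 7.44 |

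The chance of at least one Grade 4 neutropenia in a cohort of 20 is 1 − 0.876²⁰ = 0.93. That is the chance that such an event arises, not the chance that one is lost.

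If the worst result within a visit number is used, the number shown is n × p whatever f is.

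**The case against.** The case for leaving the plan alone has four parts.

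- **The selected value need not be lower or recovered.** A reader might infer that the rule always moves the grade down. The documents do not support that: daily repeats need only reach Grade 3, some participants never meet the retreatment criteria, and nothing prevents a later value from being worse. This stands. The rule favours the lower grade systematically, not in every case.
- **Worst values are provided for.** A reader might infer that the worst-value sentence in SAP 10.3 contradicts SAP 7.2.4. It reads more naturally as a separate derivation. But no worst-grade or shift table is named to use it. The table shells are in a separate document (SAP 3) that was not available, so such a table may exist there.
- **Other outputs carry the events.** A reader might infer that cytopenias and delayed recovery would be hidden from the report. They would not be. Protocol 8.3 requires clinically significant laboratory changes to be reported as AEs. The SAP tabulates TEAEs by worst grade (10.2.1) and those leading to delay or reduction (10.2.4), summarises dose reductions and relative dose intensity (10.1.1), and lists all laboratory results. This stands, with limits: the SOC/PT tables pool Grades 3 and 4, AE tables are produced across cohorts (10.2), and the worst-grade line in 10.2.7 is not by event. None gives a Grade 4 neutropenia rate by cohort.
- **The latest Day 1 value is the one that cleared the participant for dosing.** That is a fair reason to list it, but not to let it replace the abnormal value in a grade table.

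**Conclusion.** The point holds as a conditional weakness in one safety display, and it should be fixed. Where outcome-driven repeats share the scheduled visit number, the by-visit grade table favours the lower grade and can omit Grade 4 neutropenia or thrombocytopenia. With f unknown, the illustration gives a loss of 0 to about 2.5 of 20, or 0 to 7.4 of 60 participants. It borrows a per-participant rate (not a per-visit rate) from a different population; Protocol 6.6 mandates colony-stimulating factor from Cycle 1, so the numbers here may be smaller.

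A reader might infer that Grade 4 cytopenias are erased by construction and would be reported as 0%. The documents do not support that. It is only the end of the range at f = 1. SAP 7.2.4 limits its rule to repeats with the same visit number, and both SAP 7.2.4 and SAP 10.3 recognise unscheduled visits or assessments as a separate category. Nothing says which way the daily or 48-to-72-hour repeats are entered.

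The primary ORR analysis, the futility rules and the AE endpoint are unaffected.

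**What to change.** In SAP 7.2.4:

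- For post-baseline CTCAE grade and abnormality tables, use the worst valid result among those that share a visit number.
- For by-visit means and change from baseline, use the first valid scheduled result.
- Use the latest result only when the earlier sample was technically invalid.
- Leave the baseline definition in SAP 7.2.1 as it is.

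In SAP 10.3, name a by-cohort worst post-baseline grade table (or shift table from baseline) that uses all scheduled and unscheduled results and shows Grade 4 separately. This table does not depend on how repeats are numbered.

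A wider rule, taking the worst value from one scheduled visit up to the next, is not needed. It would bring in the windowing that SAP 7.2.4 generally excludes, and would assign post-dose values to the pre-dose Day 1 visit.

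Cost: SAP wording, a derivation flag and one more table. Reported grades may look less favourable. The change is best made before database lock.
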